#### **Variables:**

- a) **Patient clinical variables**- age, sex, etiology of renal disease according to ERA/EDTA code, degree of comorbidity according to the modified Charlson Index for patients with renal disease, time on renal replacement therapy with hemodialysis.
- b) **Catheter affiliation variables** - design (twin or single), material (carbonate or polyurethane), date of insertion, date of removal, vein of insertion, previous catheter-related infections (bacteremia, tunnelitis, exit site infection).

c) **Catheter-related infections** during the follow-up period- will be defined as:

- *Bacteremia*- presence of fever (body temperature  $\geq 38^{\circ}\text{C}$ ) along with a positive blood culture, with no other focus of infection.
- *Exit site infection*- positive culture of pericatheter smear together with presence of inflammatory signs limited to 2 cm around the cutaneous exit site, with no upper extension to the catheter cuff if tunneled.
- *Tunnelitis*- appearance of inflammatory signs extending beyond 2 cm from the cutaneous exit site and in the subcutaneous tract of the catheter (tunnelitis). It may or may not be associated with fever and bacteremia, and may be accompanied by purulent exudate through the cutaneous exit site.

In case of clinical suspicion of bateremia due to fever (body temperature  $\geq 38^{\circ}\text{C}$ ), 2 blood cultures will be taken 30 minutes apart, from aerobic and anaerobic germs, directly from the arterial branch of the catheter.

The exit orifice will be inspected at each dressing, and the nurse in charge will take a photograph of it before performing the dressing, to check for the presence of signs of infection by the investigating team. In the presence of signs of infection, a culture of the pericatheter smear will be taken before the exit site is cured.

d) **Patient satisfaction** with the treatment regimen. - Patients will be surveyed after the follow-up period of the study about discomfort related to the type of treatment: pain on withdrawal, presence of pruritus, loss of adherence, alteration of body image, degree of comfort. To assess these aspects, SCALE 18 Degree of perception of positive expectations, of the NOC taxonomy (5-point Likert-type scale where 1- Not at all satisfied, 2- Somewhat satisfied, 3- Moderately satisfied, 4- Very satisfied, 5- Completely satisfied) will be used.

e) Incidence of dressing-related skin alterations. - will be assessed at each hemodialysis session, using the following NOCs:

- [110115] Skin lesions
- [110121] Erythema

SCALE 14 Degree of a negative or adverse condition or response (Severe - Substantial - Moderate - Mild - None)

**Data collection and analysis:** An Excel-type data collection sheet will be created with the variables to be studied. The variables will be introduced by a member of the research team and will be extracted from the patients' clinical records (clinical reports, dialysis evolution sheets, catheter evolution sheets and analytical results). The survey of satisfaction with the treatment will be carried out by a member of the research team at the end of the follow-up period.

A descriptive analysis of the variables under study will be performed: in the case of quantitative variables, measures of central tendency and dispersion appropriate to the distribution and their 95% confidence intervals will be calculated; in the case of categorical variables, the frequency and percentage will be calculated. The catheter-related infection rate (bacteremia, exit site infection and tunnelitis) will be calculated using the following formula: number of catheter-related infections/ days of follow-up  $\times 1000$ ; both for the total number and by intervention group and type of catheter. In the case of comparisons between categorical variables, the chi-square test or Fisher's exact test will be used when necessary. Continuous variables will be compared using Student's t-test or Mann Whitney U-test, depending on their distribution. For the study of variables associated with the presence of catheter-related infections, a multiple logistic regression analysis will be performed including as independent variables age, sex, etiology of renal disease, degree of comorbidity, time on renal replacement therapy with hemodialysis,

type and model of catheter, duration of the catheter, location, and presence of previous catheter-related infections. The results will be considered significant if the critical level observed is less than 5% ( $p<0.05$ ). Statistical analysis will be performed with the PSPP statistical package.

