## **Methodology**

**Design:** Experimental, controlled and randomized study. Patients will be randomized from sealed envelopes. These envelopes will contain the outflow orifice treatment group to which each patient will be assigned. The envelopes will be numbered and the patients will be included consecutively. The contents of the envelopes will be made by a person outside the research team. A member of the research team will invite the patient to participate in the study, informing him/her of the details of the study orally and in writing (see patient information sheet), after his/her acceptance and signature of the informed consent, the patient will be randomized. Duration: November 2020 to December 2022.

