### **Intervention:**

- Cure guideline control group- cleansing exit orifice with physiological saline (0.9%), drying with sterile gauze, disinfection with 2% water-based chlorhexidine solution, environmental drying for 30 seconds and covering with self-adhesive semi-permeable polyurethane dressing.
- Cure guideline experimental group - cleaning of the exit orifice with physiological saline (0.9%), drying with sterile gauze, application of a semi-permeable polyurethane dressing with 2% self-adhesive chlorhexidine gluconate, centering the chlorhexidine gluconate band well in the exit orifice.

Outflow orifice curettage will be performed by experienced nurses from our hemodialysis unit, after a briefing on the study methodology. In both cases the treatment will be performed weekly (first day of the week), or whenever there is exudate from the exit site or detachment of the dressing; before connecting the catheter to the hemodialysis monitor. In both cases, the treatment will be carried out under maximum aseptic measures: previous hand hygiene, sterile material and treatment, and use of masks by the patient, nurse and nursing assistant. The connection to the hemodialysis monitor will be performed under these aseptic measures, covering the connection between the lines and the catheter with gauze impregnated with 2% water-based chlorhexidine solution and a sterile cloth. In addition, a bioconnector is used for hemodialysis catheters.

**Population:** patients on renal replacement therapy with hemodialysis whose vascular access is an indwelling catheter. Fifty patients will be included (25 patients in the control group - chlorhexidine 2% solution and covered with self-adhesive transparent polyurethane dressing - and 25 patients in the experimental group - with self-adhesive ACG dressings). The sample size calculation was performed with the GRANMO program version 7.12, accepting an alpha risk of 0.05 and a beta risk of 0.2 in a bilateral contrast, to detect as statistically significant the difference between two proportions, which for the control group is expected to be 25% and the experimental group 5%. A loss-to-follow-up rate of 10% has been estimated.

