#### **Exclusion criteria:**

- Allergy or hypersensitivity to chlorhexidine or polyurethane dressing
- Use of a non-tunneled venous catheter as vascular access.
- Active catheter-related infection at the time of inclusion in the study.

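### Two of the three primary-outcome components depend on judged inflammatory signs, and no masking to arm is described for the team that checks the photographs

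*Combined protocol and SAP*

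**What the plan says.** The primary comparison is of catheter-related infections: bacteremia, exit-site infection and tunnelitis (Hypothesis; Objectives). Variables, item c), defines them as follows.

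- Tunnelitis: "appearance of inflammatory signs extending beyond 2 cm from the cutaneous exit site and in the subcutaneous tract of the catheter". No culture is required.
- Exit-site infection: "positive culture of pericatheter smear together with presence of inflammatory signs limited to 2 cm around the cutaneous exit site". The smear depends on signs having been noticed; only then does the plan say that "a culture of the pericatheter smear will be taken before the exit site is cured".
- Bacteremia: fever plus a positive blood culture with no other focus. This does not depend on the photographs.

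At each dressing the nurse "will take a photograph of it before performing the dressing, to check for the presence of signs of infection by the investigating team". Data collection and analysis then has a research-team member extract the variables from clinical records.

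The one step given to someone independent is in Methodology, Design: "The contents of the envelopes will be made by a person outside the research team". That protects allocation, not outcome assessment. The dressings are visibly different, since the experimental procedure includes "centering the chlorhexidine gluconate band well in the exit orifice".

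**The concern.** Whether signs are present is a judgement, and the same finding has two possible homes in the data. Erythema and skin lesions are graded as dressing-related skin alterations (Variables, item e), while redness at the exit site can also count as an inflammatory sign of infection (item c). The plan gives no rule for choosing between them and describes no masked reader to make the choice.

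The smear is a partial guard. It protects exit-site infection against signs being over-called, but not against signs being discounted, because discounted signs lead to no smear. Tunnelitis has no culture guard at all.

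The plan also does not say which source prevails if the team's photograph reading and the chart entry disagree. A reader who knew the arm and the hypothesis could lean either way on borderline cases, and the report would give no means of detecting it. At stake is the credibility of the estimated effect on the primary outcome and, less often, the significance claim.

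**Working it through.** **Inputs.** From Population: 25 patients per arm, 25% control risk, 5% experimental risk. From Data collection and analysis: significance at p<0.05; chi-square, or Fisher's exact test where needed. Assumed, because the documents give no figure: the share s of infected patients counted only on signs-dependent components (40–80%), and the proportion m of those discounted in the experimental arm (10–30%).

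**1. Planned counts.** 25 × 0.25 = 6.25 and 25 × 0.05 = 1.25 infected patients, about 6 against 1. These cover the whole composite, including bacteremia, so only an unknown part is open to photograph reading.

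**2. Neighbouring results, 25 per arm, two-sided p.** The rate column is an exact test assuming equal follow-up days.

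| Control v experimental | Fisher | Uncorrected chi-square | Exact rate test |
|---|---|---|---|
| 6 v 1 | 0.098 | 0.042 | 0.125 |
| 7 v 1 | 0.049 | 0.021 | 0.070 |
| 6 v 0 | 0.022 | 0.009 | 0.031 |

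Moving from 6 v 1 to 6 v 0 changes significance under Fisher and under the rate test. Moving from 6 v 1 to 7 v 1 does so under Fisher only.

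**3. One signs-dependent experimental event discounted.** Take independent binomial counts a (control) and b (experimental) at 25% and 5%. Select results where Fisher p≥0.05 at (a, b) but there is significant benefit at (a, b−1). Weight each by the chance that at least one of the b events depends on signs:

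Σ P(a, b) × [1 − (1 − s)^b]

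The qualifying results have total probability 0.0667 for b=1 (6 v 1), 0.0667 for b=2 (7 v 2, 8 v 2), 0.0111 for b=3 (9 v 3, 10 v 3) and 0.0005 for b=4.

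- s=0.4: 0.0667×0.4 + 0.0667×0.64 + 0.0111×0.784 + 0.0005×0.870 ≈ 0.079
- s=0.8: 0.0667×0.8 + 0.0667×0.96 + 0.0111×0.992 + 0.0005×0.998 ≈ 0.129

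So one discounted event would turn a non-significant result into a significant benefit in about 8–13% of trials.

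**4. Systematic discounting with no true effect.** Both true risks are 25%, and the observed experimental risk is 0.25 × (1 − s × m).

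| s, m | Observed risk | Observed RR | False benefit (Fisher) | Total two-sided error |
|---|---|---|---|---|
| no bias | 0.25 | 1.00 | 1.1% | 2.2% |
| 0.4, 0.1 | 0.24 | 0.96 | 1.3% | 2.2% |
| 0.8, 0.3 | 0.19 | 0.76 | 3.7% | 3.9% |

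**5. Wider fragility, for contrast.** Allow any one patient, in either arm and either direction, to be reclassified. Fisher significance then changes in 37.7% of trials at 25% versus 5% (19.1% into significance, 18.6% out of it). This count includes bacteremia and directions that misreading a photograph could not produce. Fisher power at 25 per arm is 37%.

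**The case against.** **Fragility is a sample-size matter.** A reader might take the 37.7% as the size of the masking problem. It is not. It counts every event type in both arms and both directions, and it would remain with perfect masking because it comes from 25 patients per arm. This objection stands. The figure for the mechanism at issue is the 8–13% in step 3, and that too rests on an assumed share of events.

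**The test is not settled.** The plan does not assign Fisher's test to the primary comparison, and it also defines the outcome as a rate per 1000 days. Under an exact rate test, 7 v 1 is not significant. This stands as a limit on the Fisher-based figures.

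**Unmasked reading is not stated.** A reader might infer that the team knows the arm, or that the photographs show it because the old dressing is still on. The documents say neither. The photograph is of the exit orifice, which is also inspected at each dressing, so an uncovered site is the natural reading. What can be said is that no masking is described.

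**Some signs are already recorded.** Erythema and skin lesions are graded at every session, so part of the by-arm picture exists. This stands, but those grades do not show how many smears were taken or were positive. A lower culture yield under the chlorhexidine band might also be suspected; the documents give nothing to support or size it.

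**Bedside care cannot reasonably be masked.** This is true, and it limits the remedy, but it does not prevent masked reading of photographs that are already planned.

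**Conclusion.** The point holds as an omission that should be put right. Tunnelitis, and the signs part of exit-site infection, rest on judgement; no masking of the readers is described; and the deciding source is not stated. Bias could run in either direction, and its amount is unknown.

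Under the stated assumptions the harm is mainly to the estimate: with no true effect the observed risk ratio could fall to between 0.96 and 0.76. False benefit rises only modestly, and total error stays below the nominal 5%. The documents do not support a claim that unmasked reading would often decide the trial's conclusion, or that misreading is likely. Nor do they give the share of events that are bacteremia, which is outside the photograph's reach.

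**What to change.** Keep the three definitions, the sample size and bedside care as planned, and add the following.

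- Photograph the uncovered exit site and store the image under a code that does not carry the arm.
- Have an existing team member who did not dress that patient read it without knowing the arm.
- State that this masked reading decides the signs part of exit-site infection and tunnelitis for the analysis. Use the bedside note, with dressing details removed, only for signs that a photograph cannot show.
- Report by arm the number of sites with signs, smears taken and smears positive, as a supportive table.

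**Cost.** Photographs, readers and smears are already planned. The extra work is coding images, preparing some notes and producing one table; no additional dressings, patients or visits are needed.

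**What it does not cure.** Skin marks may reveal the arm. The bedside decision to take a smear stays unmasked, so for exit-site infection the masked reading can remove events but cannot add one where no smear was taken. Bedside notes still carry the unmasked nurse's judgement. The fragility due to the small sample is untouched.

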### **Secondary:**

- The degree of comorbidity, previous infections, time on renal replacement therapy, and catheter duration will correlate with a higher rate of catheter-related infections.
- Hemodialysis catheter exit site dressing with AGC dressings will correlate with higher patient satisfaction than dressing with 2% chlorhexidine solution and covered with a self-adhesive semi-permeable polyurethane dressing.

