### **Secondary:**

- To evaluate factors related to the incidence of hemodialysis catheter-related infections.
- To evaluate the incidence of dressing-related skin alterations.
- To assess patient satisfaction with regard to the type of hemodialysis catheter exit site dressing.

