### **Ethical considerations**

Approval of the project will be requested from the Cantabria Drug Research Ethics Committee (CEIm de Cantabria). The research team declares that it has no conflict of interest with respect to the products used in the study.

All patients will be passed the Information and Informed Consent Sheet prior to their inclusion in the study, such consent will be made based on the provisions of Regulation (EU) 2016/679 of the European Parliament and of the Council of 27 April 2016 on Data Protection (RGPD); and the Organic Law 3/2018, of December 5, on the Protection of Personal Data and guarantee of digital rights.

The research will be conducted on the basis of the Declaration of Helsinki, complying with the standards of Good Clinical Practice (GCP) as applicable.

Those patients who wish to receive the intervention but not participate in the project will be provided with the same intervention as the experimental group.

The custody of all documentation related to the project will be carried out by the principal investigator of the project, for a period of 5 years, after which it will be destroyed following the standardized procedure.

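### The team that predicts higher satisfaction with the new dressing also runs the satisfaction survey, with no masking, self-completion or neutral administration described

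*Combined protocol and SAP*

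**What the plan says.** Under Hypothesis, Secondary, the protocol makes a directional prediction: "Hemodialysis catheter exit site dressing with AGC dressings will correlate with higher patient satisfaction than dressing with 2% chlorhexidine solution", the control site then being covered with a plain polyurethane dressing. The matching secondary objective is "To assess patient satisfaction with regard to the type of hemodialysis catheter exit site dressing".

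Variables, item d, describes the measurement: "Patients will be surveyed after the follow-up period of the study about discomfort related to the type of treatment". The aspects listed are pain on withdrawal, pruritus, loss of adherence, body image and comfort. The instrument is a "5-point Likert-type scale where 1- Not at all satisfied", running up to 5 for complete satisfaction.

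The Data collection and analysis paragraph names who does it: "The survey of satisfaction with the treatment will be carried out by a member of the research team", at the end of follow-up. The same paragraph sets p<0.05 as the criterion for significance and gives general rules for comparing continuous and categorical variables. It has no rule specific to satisfaction.

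On allocation, Methodology (Design) says only "Experimental, controlled and randomized study. Patients will be randomized from sealed envelopes". Someone outside the team prepares the envelopes, and that is the only task the protocol gives to an outsider. The limitations section names the three-month follow-up and nothing else.

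**The concern.** The group that has written down the answer it expects also collects that answer. The answers are subjective ratings given once, with no external check of the kind that a culture provides for bacteremia and exit site infection. Randomization makes the arms comparable at entry, but it does not protect against a bias that enters when the outcome is measured.

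At stake is the secondary conclusion on satisfaction. If the person running the survey knows the arm and the prediction, tone, prompting or the patient's wish to please could move scores by different amounts in the two arms. A significant difference might then reflect how the survey was run and not the dressing.

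**Working it through.** **1. What the text establishes.**

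| Element | Where | Stated? |
|---|---|---|
| Directional prediction for satisfaction | Hypothesis, Secondary | Yes |
| Survey carried out by a research team member | Data collection and analysis | Yes |
| Subjective 5-point ratings, collected once after follow-up | Variables, d | Yes |
| Masking of patients, nurses or surveyor | Anywhere | No |
| Self-completion, fixed script or outside surveyor | Anywhere | No |
| Face-to-face questioning | Anywhere | No; mode left open |

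The first five rows give a route for bias and no safeguard against it. The last row means that the route depends on how the survey is run.

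**2. When a shift matters.** Let the survey add *a* points to the mean in the experimental arm and *b* points in the control arm. With no true difference, the expected observed difference is *a* − *b*. If *a* = *b*, nothing is created. Only the differential part, δ = *a* − *b*, can produce a false finding.

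**3. Illustration of size.** The plan has no figure for satisfaction to reproduce.

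Inputs from Methodology (Population) and Data collection and analysis: 25 per arm, 10% loss, two-sided 5% level. Completers per arm: 25 × 0.90 = 22.5, taken as 22.

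Assumed, because the documents give no value: SD 0.8 to 1.2 points; δ = 0.25 or 0.5 points; a t-test on a single item; no true difference.

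Standard error = SD × √(2/22). Noncentrality = δ / standard error. Degrees of freedom = 42, critical value 2.018. The chance of p<0.05 is the two-tailed rejection probability of the noncentral t distribution.

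| SD | Standard error | δ = 0.25: noncentrality, chance | δ = 0.5: noncentrality, chance |
|---|---|---|---|
| 0.8 | 0.241 | 1.036, 17.3% | 2.073, 52.6% |
| 1.0 | 0.302 | 0.829, 12.8% | 1.658, 36.7% |
| 1.2 | 0.362 | 0.691, 10.4% | 1.382, 27.2% |

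With δ = 0 the chance is 5% in every row. The ranges are therefore about 10% to 17% for a quarter of a point and about 27% to 53% for half a point, per item.

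**The case against.** The strongest reply is that the protocol never says the questions are put to the patient aloud. A team member who hands out and collects a form also carries out a survey, so self-completion may already be intended. This stands: a reader might infer an interview, but the documents leave the mode open. It does not remove the point, because no safeguard is described for either mode and one sentence would settle the matter.

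Second, the percentages assume the bias whose effect they show. This also stands. They say what a shift of a given size would do, not that one will occur. The plan does not say whether the items will be treated as continuous or categorical, or tested singly, so the per-item t-test is an assumption too.

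Third, patients are not described as masked, so their own expectation remains whatever the mode. That is true, but influence from the surveyor is a separate source and can be reduced even if expectation cannot.

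Two stronger readings should be resisted:

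- A reader might take the undertaking in Ethical considerations as proof that the team prefers the new dressing: "Those patients who wish to receive the intervention but not participate in the project will be provided with the same intervention as the experimental group". It is compatible with such a preference but does not establish one.
- A reader might carry the doubt over to the infection result. The survey plays no part in how infections are defined or detected, so the documents do not support that.

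**Conclusion.** The point holds as a modest, avoidable risk of measurement bias in a secondary outcome. The documents establish the directional prediction, the team-run survey and the absence of any described safeguard. They do not establish that the survey is an interview, that any bias will occur, or how large it would be. Harm requires a surveyor effect that differs between arms. If there were one, a shift of half a scale point or less would be enough in a trial this small to raise the chance of a false positive well above 5%, under the assumptions set out in the working. The primary infection comparison and the sample size are not touched. This is a low-cost improvement and not a serious flaw.

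**What to change.** Amend Data collection and analysis so that patients complete the satisfaction form themselves on paper at the end of follow-up. The form carries the study number only and is returned in a closed envelope. Where a patient needs help, it comes from someone outside the research team, such as a relative, and is recorded on the form. The team enters the scores but does not put the questions.

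Add to the limitations section that patients are not masked, so their own expectation of the dressing remains a possible influence on satisfaction.

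The cost is a printed form and an envelope per patient; no extra interviewer is needed. The downsides are some missing items and some patients needing help. The gain is also partial: a study number can still be linked to the arm by the team, and a helper may have some influence, which is why help should be recorded.

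### The plan allows chi-square or Fisher for proportions with no criterion, and at 25 per arm the two often disagree; naming one unconditional exact test in advance is a cheap, minor improvement

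*Combined protocol and SAP*

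**What the plan says.** In the Population paragraph, the aim of the sample size calculation is "to detect as statistically significant the difference between two proportions"; the planning rates are 25% under control and 5% under the experimental dressing. The error risks are stated separately: "accepting an alpha risk of 0.05 and a beta risk of 0.2 in a bilateral contrast". On numbers the paragraph says "Fifty patients will be included (25 patients in the control group"; the other arm also has 25. On losses it says "A loss-to-follow-up rate of 10% has been estimated".

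The Data collection and analysis paragraph gives one rule for comparing categorical variables: "the chi-square test or Fisher's exact test will be used when necessary". Results count as significant when p is below 0.05. The plan does not say what triggers Fisher or whether chi-square is continuity-corrected, and it does not assign either test to the primary comparison. The same paragraph defines an infection rate per 1000 days of follow-up but names no test for it.

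**The concern.** These are the only tests the plan offers for the quantity on which it is sized. With 25 per arm and about 7 infected patients expected, the p-values of chi-square and Fisher differ by a factor of two or more, and the 0.05 threshold often falls between them. A reader of the results could not tell from the plan which p-value was the planned one.

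There is also a cost in power. The usual reading of such a sentence sends most trials of this size to Fisher, which is very conservative with few events. Using uncorrected chi-square throughout avoids that loss, but only by going slightly above 5%.

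**Working it through.** **Inputs.** From the Population paragraph: rates 0.25 and 0.05, two-sided alpha 0.05, beta 0.2, 25 per arm, 10% loss (about 22 to 23 evaluable per arm). From Data collection and analysis: chi-square or Fisher, p < 0.05. My assumption, because the plan gives no trigger: Fisher if any expected count is below 5, otherwise uncorrected chi-square. I call this the rule.

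**The plan's own figure.** With the pooled two-sided formula, n per arm = [1.96·√(2·0.15·0.85) + 0.842·√(0.25·0.75 + 0.05·0.95)]² / 0.20² = 48.8, so 49 per arm, or 49/0.9 = 54.4, so 55 after losses. The stated 25 per arm is not reproduced; approximate power at 25 per arm is 51%. That is a separate and larger problem. Here it only sets the scale.

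**Single tables at 25 per arm.** The planned rates give 6.25 and 1.25 expected infected patients, so the nearest table is 6 against 1.

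- Chi-square, 6 v 1: pooled rate 7/50 = 0.14; SE = √(0.14·0.86·2/25) = 0.0981; z = 0.20/0.0981 = 2.04; p = 0.042.
- Fisher, 6 v 1: 2·[C(25,6)·25 + C(25,7)]/C(50,7) = 2·4,908,200/99,884,400 = 0.098.
- Chi-square, 5 v 0: z = 0.20/√(0.1·0.9·2/25) = 2.36; p = 0.018.
- Fisher, 5 v 0: 2·C(25,5)/C(50,5) = 2·53,130/2,118,760 = 0.0502.
- Barnard, pooled z (the maximum, over the common rate, of the probability of a |z| at least as large): 0.053 for 6 v 1 and 0.021 for 5 v 0.
- Neighbouring table 7 v 1: chi-square 0.021, Fisher 0.049, so both are significant.

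**How often the listed tests disagree.** Summing binomial probabilities at 25% and 5% over all tables, chi-square is significant and Fisher is not in 18.5% of trials at 25 per arm, and in 14% at 22 or 23 per arm.

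**How often the rule uses Fisher.** With equal arms the smallest expected count is half the number infected, so Fisher applies when 9 or fewer patients are infected. At the planned rates the probability of this is 0.80 at 25 per arm, 0.87 at 23 and 0.90 at 22.

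**Power at 25% v 5%, all tables enumerated.**

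| Control/experimental | Rule | Barnard | Gain (points) |
|---|---|---|---|
| 25/25 | 0.410 | 0.481 | 7 |
| 24/24 | 0.428 | 0.461 | 3 |
| 23/23 | 0.399 | 0.440 | 4 |
| 22/22 | 0.371 | 0.419 | 5 |
| 24/23 | 0.409 | 0.473 | 6 |
| 23/22 | 0.385 | 0.453 | 7 |
| 22/23 | 0.479 | 0.479 | 0 |

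At 25 per arm the gain comes from two tables that Fisher misses and Barnard does not: 4 v 0 (probability 0.033) and 5 v 0 (0.046). Against this, 9 v 3 (0.007) is significant under the rule and not under Barnard (p = 0.055). Net: 0.033 + 0.046 − 0.007 = 0.072, which agrees with the table within rounding.

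**Type I error at 25 per arm.**

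| Test | Common rate 15% | Common rate 25% | Maximum |
|---|---|---|---|
| Chi-square, uncorrected | 0.055 | 0.054 | 0.065 |
| Fisher | 0.019 | 0.022 | 0.033 |
| Rule | 0.028 | 0.051 | 0.065 |
| Barnard | 0.038 | 0.042 | 0.046 |

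The 0.065 maximum occurs at a common rate near 50%. At 22 per arm the rule's maximum is 0.049. Barnard's maximum is at most 0.0491 in every configuration in the power table.

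**The case against.** Chi-square with Fisher for sparse tables is conventional wording, and Fisher is a valid test. Five points on that side deserve an answer.

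- A reader might infer that the plan fails to hold its 5% level. At the planned rates the documents do not support that. Under the assumed rule the error is 0.028 at a 15% common rate and only 0.051 at 25%; 0.065 needs a rate near 50%, far from anything the plan expects. At 22 per arm the rule never exceeds 5%. This objection stands.
- A reader might also infer that the analyst would pick the test after seeing which one is significant. The plan does not say so. An expected-count trigger, with equal arms, depends on the total infected and not on the difference between arms. But that trigger is an assumption too. What the text supports is that the choice is not fixed.
- The replacement does not change the conclusion for 6 v 1: Fisher gives 0.098 and Barnard 0.053, and neither is significant. This stands. The benefit is one predetermined answer, not a favourable one.
- The gain rests on a few tables and vanishes at 22/23. Barnard is not the only candidate: Boschloo's test has power 0.439 at 22 per arm against Barnard's 0.419, but 0.395 at 23 against 0.440. Both points stand. Uncorrected chi-square has more power still (0.556 at 25 per arm), but its error is slightly above 5%.
- The main objective is worded as a rate, so applying these tests to the primary comparison is an inference from the sizing. This stands, and it limits the fix to the proportion.

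**Conclusion.** The point holds as a minor, inexpensive improvement. The plan leaves open which of two tests applies to the quantity it is sized on, and at 25 per arm that matters in about 18% of trials at the planned rates. Against the conventional reading, Barnard's test matches or improves power in all seven configurations checked, by 3 to 7 points for equal arms and 0 to 7 for slightly unequal ones, with maximum error below 0.05.

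This rests on the plan's 25% and 5%, on 22 to 25 evaluable patients per arm, on a binary endpoint of at least one infection per patient, and on the assumed expected-count trigger. The 18% disagreement at 25 per arm does not need that trigger, only that chi-square is uncorrected. It would be wrong to conclude that the plan has a serious type I error problem or that a better test rescues it: power stays below 50% under Barnard in every configuration, against the 80% planned.

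**What to change.** In Data collection and analysis, state that the proportion of patients with at least one catheter-related infection will be compared between arms by Barnard's unconditional exact test with the pooled z statistic, two-sided at 5%. A sponsor who prefers another test should still name exactly one before the data are seen.

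The cost is one sentence and no extra patients or data. It may need a free statistical package beside PSPP. The sample size and the test for the rate per 1000 days remain open and need their own corrections.
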